7.11 Storage and analysis of samples

A portion of the stool sample (1-2ml) provided for routine clinical investigation at the initial presentation or at 3 months follow-up will be separated and stored at -20°C for the measurement faecal VOCs. If there is inadequate stool, or the consent to participate in the study is provided at a later date, a further stool sample will be requested. The study sites will be responsible for ensuring that samples are appropriately labelled. Stool samples will be stored at the participating centres and shipped frozen in batches for analysis of VOCs performed at the end of the study in the [name] Lab, University of Liverpool. VOCs will analysed by two methods:

- i) headspace SPME-Combipal GCMS
- ii) the GC-sensor "Odoreader©".

The first method results in the semi-quantative identification of specific VOCs. Gases are released by heating 450mg of faeces aliquotted into 10ml headspace vials for 30mins at 60°C. The headspace gases will be adsorbed onto a DVB-CAR-PDMS solid phase microextraction (SPME) fibre. The fibre will be used to introduce the VOCs in to the gas chromatography column before they are fragmented in the mass spectrometer (Perkin Elmer). The fibre desorption conditions are 5 minutes at 220°C. The initial temperature of the GC oven will be set at 40°C and held for 1 minute before increasing to 220°C at a rate of 5°C/min and held for 4 min with a total run time of 41 min. A solvent delay is 6 min and the MS will be operated in electron impact ionization El+ mode, scanning from ion mass fragments 10 to 300 m/z with an interscan delay of 0.1 sec and a resolution of 1000 at FWHM (Full Width at Half Maximum). The helium gas flow rate is set at 1 ml/min. The sensitivity of the instrument had been determined using 2-pentanone; the limit of detection is 3 times the signal/noise ratio for 2-pentanone with the DVBCARPDMS fibre is 16 ppm.

The data (chromatograms and fragmentation patterns) will be analysed using AMDIS software and the current NIST library of over 240,000 compounds. Project–specific libraries of compounds will be used to generate reports for each group of children – those with CD, UC and other pathologies. Metab software (Aggio 2011) will be used to align the reports. Metaboanalysis software (Xia 2009) will be used to compare the abundance of each VOC in each group: the software will report the false discovery rate (FDR) allowing comparison of datasets of this kind. ANOVA will be performed in the same way. We will produce summaries of the data describing the fold changes, FDR, sensitivity, specificity and ROC curves for compounds and models derived from them. This method uses equipment that is available in hospital clinical chemistry laboratories.

For the second method, the stool sample will be analysed by our GC-sensor (Odoreader©). This is more rapid than the first method and generates a VOCs profile (rather than identifying individual VOCs). 450mg of faeces are heated within the device, and the emitted gases passed through a GC column. On leaving the column, the VOCs pass perpendicular to a metal oxide sensor unit. A current is passed across the sensor and its resistance is determined by the presence of VOCs. Consequently the sensor output (current) is a representation of the VOCs in the sample (with an output similar to a chromatogram). We have a well-defined algorithm that removes the baseline, normalises the data and performs retention time correction before comparing the profiles derived from two groups of samples using wavelets. The data is then reported as sensitivity, specificity and AUROC of a model using state of the art modelling tools including support vector machine polynomial (SVMpoly) with double cross validation and Monte Carlo randomisation (Aggio 2016).

Stool samples will be stored frozen for up to 5 years for possible use in ancillary studies. Stool samples collected from participants as part of this study will be transported, stored, accessed and processed in accordance with national legislation relating to the use and storage of human tissue for research purposes and such activities shall at least meet the requirements as set out in the 2004 Human Tissue Act and the 2006 Human Tissue (Scotland) Act.

In the version of the protocol, we will also investigate the fungal mycobiome.

Stool samples metagenome is extracted with two kits (200 mg with each kit): 1) PSP Spin Stool DNA Plus Kit (Stratec) with an extra bead beating step of 6 minutes with 0.1 and 0.5 mm zirconia beads; 2) QIAamp Fast DNA Stool Mini Kit (QIAGEN). DNA is quantified with a Qubit (Qubit dsDNA HS assay Kit, Life Technologies) and an equimolar amount from each extraction is merged. This is the template for gene quantification (Liu 2012). The same primer set are then used for the production of amplicons for MiSeq Illumina sequencing. To achieve this, a universal tail tag dual index barcoding approach D'Amore 2016) is used. This is a 2-step PCR, where amplicons specific primers with a universal tail are used during the first PCR, and then a second amplification is used to insert the tag and the sequencing adaptor to the amplicons. Amplicons are purified with AxyPrep Mag PCR Clean-up kit (Axygen) and quantified with the same method mentioned for the genomic DNA. Samples are then run in a fragment analyser, pooled, size-selected and sequenced. Sequencing is carried out using a 2X250bp MiSeq kit in the Centre for Genomic Research (CGR). Reads are de-multiplexed, trimmed (Cutadapt) (Martin 2011) and filtered by the CGR. Further analyses are done with a pipeline developed by the

EudraCT number: TBC

CGR for bacterial 16S rRNA and adapted by us to analyze eukaryotic 18S rRNA. This include an errorcorrection with Bayes-Hammer (Nikolenko 2013), filtering out of PhiX DNA, merging the pair-reads with Pear (Zhang 2014). Further manipulation leads to OTUs picking with Swarm (Mahe 2015). QIIME (Caporaso 2010) is then used for taxonomy assignment (BLAST algorithm (Altschul 1990) and SILVA (Quast 2013)), alignment, phylogeny and evaluation of alpha diversity. Last is beta diversity analysis, this is achieved with Non-metric multidimensional scaling (NMDS) with Bray-Curtis matrix distance (Torondel 2016).

- 7.12 End of trial: N/a
- 8 TRIAL MEDICATION: N/a
- 8.1 Name and description of investigational medicinal product(s): N/a
- 8.2 Legal status of the drug: N/a
- 8.3 Summary of Product Characteristics (SmPC): N/a
- 8.4 Drug storage and supply: N/a
- 8.5 Preparation and labelling of Investigational Medicinal Product: N/a
- 8.6 Dosage schedules: N/a
- 8.7 Dosage modifications: N/a
- 8.8 Known drug reactions and interaction with other therapies: N/a

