5 STUDY SETTING

Recruitment of children will be undertaken in 3 paediatric gastroenterology referral centres in the UK: Alder Hey Children's Hospital, Liverpool; Bristol Royal Hospital for Children, Bristol; and Birmingham Children's Hospital, Birmingham.

Laboratory analyses and statistical analysis to determine and compare faecal VOCs between groups will be done in the Institute of Translation Medicine, University of Liverpool. Management and analysis of clinical data will take place at the Liverpool School of Tropical Medicine.

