7.3 The randomisation scheme: N/a

7.3.1 Method of implementing the allocation sequence: N/a

7.4 Blinding

Laboratory staff performing the faecal VOCs analysis will be blinded to the patient's diagnosis and response to treatment in those with IBD.

Faecal VOCs results will not be available to clinical staff who are making diagnoses and assessing response to treatment in IBD.

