10.9 Other statistical considerations

In addition to the main analyses described above, we also plan to undertake extensive statistical analysis to explore whether combining VOC data with faecal calprotectin and possibly other inflammatory markers (e.g. CRP) increases sensitivity and specificity in the diagnosis of IBD. Multivariate logistic regression models will be used to determine the specificities and 95% confidence intervals of combinations of diagnostic tests and also explore the effects of demographic factors such as age, sex and region. Other statistical methods will be used if deemed necessary.

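### GCMS accuracy is to be reported for models built from compounds selected in the same children, with no internal validation stated, although the GC-sensor model has double cross-validation

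*Protocol*

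**What the plan says.** Protocol 3.4 names two measurements of the primary outcome, GCMS and the GC-sensor. Section 7.11 describes an analysis chain for each.

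- **GCMS.** Project-specific compound libraries are used to "generate reports for each group of children – those with CD, UC and other pathologies". Next, "Metab software (Aggio 2011) will be used to align the reports". The abundance of each compound is then compared between groups with an FDR. Finally, "We will produce summaries of the data describing the fold changes, FDR, sensitivity, specificity and ROC curves for compounds and models derived from them". No cross-validation, resampling or hold-out set is mentioned.
- **GC-sensor.** Sensitivity, specificity and AUROC come from a support vector machine model "with double cross validation and Monte Carlo randomisation".

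Section 10.3.2 keeps the same split. For GCMS it expects to find a small set of diagnostic compounds in this cohort; for the sensor it refers to the published advanced methods. Section 10.7 includes every participant with a completed VOC analysis. Section 10.9 adds logistic models that combine VOCs with calprotectin (FC) and possibly CRP, "to determine the specificities and 95% confidence intervals of combinations of diagnostic tests".

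On blinding, section 7.4 states: "Laboratory staff performing the faecal VOCs analysis will be blinded" to diagnosis and treatment response. Section 5 says "Laboratory analyses and statistical analysis to determine and compare faecal VOCs between groups will be done" in one university institute, while section 11.2 gives data analysis to the study statistician. Section 10 refers to a separate SAP.

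**The concern.** If compounds are chosen because they separate the groups in these children, and a model built from them is then scored on the same children, its sensitivity, specificity and AUC are too favourable. The data have been used twice. FDR control limits the share of falsely declared compounds; it does not correct the accuracy of a model fitted to the declared ones.

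Three things are at stake:

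- The two primary measurements would be reported on different footings, and GCMS could look better than the sensor only because it was not cross-validated.
- The sample size in 10.1 rests on VOC specificity exceeding that of FC by 0.12, and optimism works in the direction of that claim.
- If VOCs chosen in these children enter the combined models of 10.9, the optimism goes with them.

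The blinding question is separate. Reports grouped by CD, UC and other pathologies, produced before alignment, use the diagnosis while the feature table is still being built. The protocol does not say how this fits with 7.4.

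**Working it through.** **1. The plan's own figure.** Section 10.1 gives 88 children for specificity 0.80 v 0.68, 80% power, 0.05 level. A one-sample test against a fixed 0.68, two-sided, with variance at the alternative, gives

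n = 0.80 × 0.20 × ((1.960 + 0.842) / 0.12)² = 87.2, rounded up to 88.

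The figure reproduces, so this point rests on no arithmetic error. The benchmark difference is 0.80 − 0.68 = 0.12.

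**2. Group sizes (10.1).** 286 children with IBD confirmed in 1 in 2 gives 286 / 2 = 143 v 143. Two-thirds CD and one-third UC gives 143 × 2/3 ≈ 95 CD and 143 × 1/3 ≈ 48 UC. This leaves none for indeterminate colitis, so the real CD v UC groups may be somewhat smaller.

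**3. Assumptions not in the protocol.** 200 independent, normally distributed compounds, of which ten are truly shifted by 0.4, 0.6 or 0.8 SD. Compounds are selected by t-test with Benjamini–Hochberg FDR at 5%, and a logistic model is fitted to those selected. Apparent AUC is taken in the same children and compared with AUC in 4,000 independent subjects, over 200 to 300 replicates per scenario. Where separate runs differed by 0.01, both values are shown.

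| Groups | Shift | Apparent AUC | AUC in new subjects | Optimism |
|---|---|---|---|---|
| 143 v 143 | 0.4 SD | 0.80–0.81 | 0.74–0.75 | 0.06 |
| 143 v 143 | 0.6 SD | 0.92 | 0.90 | 0.02 |
| 143 v 143 | 0.8 SD | 0.97 | 0.96 | 0.01 |
| 48 UC v 95 CD | 0.4 SD | 0.75–0.76 | 0.63–0.64 | 0.11–0.13 |
| 48 UC v 95 CD | 0.6 SD | 0.89 | 0.82 | 0.07 |
| 48 UC v 95 CD | 0.8 SD | 0.97 | 0.94 | 0.03 |

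The 0.4 SD row for UC v CD is conditional on selecting something: in somewhat over 40% of those runs no compound passed the FDR threshold and there was no model to score.

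**4. Against the FC benchmark.** At 143 v 143 and 0.4 SD, with the cut-off chosen in the same children by the Youden index (also an assumption), apparent specificity was about 0.75 and specificity in new subjects about 0.68, an excess of 0.07. As a share of the difference sought, 0.07 / 0.12 = 58%.

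**5. Order of steps and blinding.** Section 7.11 puts group reports first, then alignment, then comparison. Section 7.4 blinds the staff who perform the VOC analysis. No section says who generates the group reports, or when the diagnosis is linked to the sample. The passages can be made consistent, but as written they are not.

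**The case against.** **Silence is not a decision.** A reader might infer that GCMS accuracy will be estimated without cross-validation. The protocol does not say so. It states none, and section 10 defers to a SAP where validation of derived models would ordinarily appear. That reading is therefore not supported. What remains is that the protocol itself sets out both chains and their accuracy outputs and gives validation to only one; a SAP that follows it would inherit the mismatch.

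**The blinding is not shown to be broken.** A reader might also infer a breach of 7.4, or that the same laboratory staff both run the samples and compare the groups. Neither is established. A project-specific library may be one common library, grouping may follow blinded acquisition, and someone else may do it. Section 5 names a shared institute, not shared staff, and 11.2 gives data analysis to the study statistician. Any group comparison needs the diagnosis at some point. What stands is narrower: grouping is placed before alignment, without a statement of who does it or when.

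**The size may be small.** The Background reports adult sensitivity of 94–96% with specificity of 80–82%, and 10.1 targets specificity 0.80. If signals in children are that strong, the main comparison is inflated by only 0.01–0.02 AUC. This objection stands, and the weak-signal figures cannot be called the expected ones. It is less reassuring for CD v UC, where 0.03–0.07 remains.

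**The study is exploratory.** Sections 3.4 and 7.2 say so, and VOC results reach neither treating clinicians nor families. This limits the consequences, but the study still reports diagnostic accuracy and is sized against a published FC specificity.

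**Conclusion.** The point holds as a defect in what 7.11 fixes. GCMS compounds are selected by group comparison, models are derived from them, and their accuracy is reported with all analysed children included and no internal validation stated; the sensor model has double cross-validation. Followed as written, GCMS accuracy would be optimistic and not comparable with the sensor figures.

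The amount cannot be fixed from the protocol, which gives no compound count, effect size or model size. Under the stated assumptions it ranges from negligible (0.01 AUC) to 0.06 in the main comparison. For CD v UC it ranges from 0.03 to 0.13, the upper end only in runs where a compound was selected. In the weak-signal case the specificity excess of about 0.07 is more than half of the advantage over FC that the study seeks. Correlated compounds or a different selection rule would change these figures. The effect on remission v persistent disease and on the combined models of 10.9 was not calculated.

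On blinding, the conclusion is only that 7.11 and 7.4 are unreconciled.

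**What to change.** In sections 7.11 and 10.3, with matching text in the SAP:

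1. Apply to GCMS the same double (nested) cross-validation already specified for the GC-sensor, with compound selection, model fitting and cut-off choice all inside the training folds. Report the resulting sensitivity, specificity and ROC as the GCMS accuracy. Fold changes and FDR from the full cohort can stay as description.
2. In the combined models of 10.9, enter out-of-fold VOC scores rather than scores fitted to the same children.
3. Identify and align all samples with one common library, blind to diagnosis; lock the feature table; only then attach diagnoses. Name who does this and when, so that 7.11 and 7.4 agree.

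The cost is protocol and SAP wording, some computing time, and somewhat lower reported accuracy, more so for CD v UC. No extra children or samples are needed. Section 7.11 places the VOC analysis at the end of the study, so the change can be made before any diagnosis is linked.

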8.9 Concomitant medication

Children will be excluded from participating in the study if they have already received treatment for IBD (e.g. polymeric formula feeds in children awaiting investigation). There are no other restrictions regarding medications.

8.10 Trial restrictions

There are no study restrictions.

- 8.11 Assessment of compliance: N/a
- 8.12 Name and description of each Non-Investigational Medicinal Product (NIMP): N/a

9 PHARMACOVIGILANCE: N/a

The study does not include an intervention. Participating in this study will not pose any risk to participants.

10 STATISTICS AND DATA ANALYSIS

A Statistical Analysis Plan will be produced separately.

10.1 Sample size calculation

Given the high sensitivity of FC in identifying children with IBD (0.98; 95% CI 0.95–1.0; Henderson 2014), we have based the sample size calculation on demonstrating that faecal VOCs have a higher specificity in identifying IBD than FC. We require 88 children with suspected IBD to demonstrate that VOCs has a better specificity of 0.80 than the specificity of 0.68 reported for FC (Henderson 2014) with 80% power at the 0.05 significance level.

Given the non-invasive nature of our study, we plan to increase the number of children recruited to also assess the ability of VOCs to differentiate between CD and UC. We plan to exceed the numbers of adults with active IBD that demonstrated excellent separation between CD and UC in our previous study (110 patients; Ahmed 2016). Our hospital IBD databases indicate that amongst new cases, two-thirds have CD and one-third UC. In our clinical experience, IBD is confirmed in 1 in 2 children with suspected IBD. To achieve sufficient power, we will recruit a total of 286 children with suspected IBD.

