(http://www.nice.org.uk/guidance/dg11) and a near-patient test has been developed (http://www.buhlmannlabs.ch/core/quantum-blue/calprotectin/). A recent meta-analysis (394 IBD/321 non-IBD controls) reported a pooled sensitivity and specificity of FC in the diagnosis of IBD in children of 0.98 (95% confidence interval: 0.95–1.0) and 0.68 (0.50– 0.86) respectively (Henderson 2014). The low specificity indicates that an alternative or additional test with higher specificity is needed to reduce the time to diagnosis and avoid many children undergoing unnecessary investigations.

There is great interest in the measurement of volatile organic compounds (VOCs) in breath and vapours from various human tissues (urine, stool, blood) in the diagnosis and monitoring of a wide range of diseases. VOCs emitted from stool are responsible for stool odour and consist of a large number of carbon based molecules of low molecular mass (<1.5Kd) including organic acids, alcohols, esters, heterocyclic compounds, aldehydes, ketones and alkanes. They result from the metabolism of the intestinal mucosa and the gut microbiota and their abundance changes according to the specific effects of intestinal diseases on these processes (Chan 2016).

We have demonstrated that faecal VOCs are relatively stable over time within and between individuals despite day-to-day variation in diet and are not affected by freezing and storage of stool samples ([name]; personal communication; PhD Thesis). We have optimized procedures for stool handling for metabolite extraction for gas chromatography-mass spectrometry (GC-MS) analysis (sample volume, solid phase micro-extraction fibre coating, extraction conditions [temperature and time] and vial volume; Reade 2014) and also developed the advanced statistical methods required for determining and comparing VOC profiles (Aggio 2016).

We have shown that the analysis of VOCs separates adult patients with diarrhoea-predominant irritable bowel syndrome (n=30) from those with active CD (62) and UC (n=48; sensitivity of 94% and 96% and specificity of 82% and 80% respectively; p<0.05). Our data in adults strongly suggests that VOCs differentiate CD from UC, and also Crohn's colitis from UC (Ahmed 2013). More recently, we have shown that VOCs also distinguish between active and inactive CD and UC in adult patients (Ahmed 2016).

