3.4 Primary endpoint/outcome

The primary endpoint/outcome is faecal VOCs at initial presentation to specialist paediatric gastroenterology review. Faecal VOCs will be measured in stool samples by two methods:

- 1. Gas chromatography-mass spectrometry (GCMS) will identify individual VOCs
- 2. The GC-sensor "Odoreader©" will generate a VOCs profile

We will explore whether the presence/absence of one or more individual faecal VOCs and VOCs profiles differ in children subsequently diagnosed to have IBD and those with non-IBD gastrointestinal disorders

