7.1.2 Screening

The clinical team will review referral information, including the results of any investigations performed to date (e.g. faecal calprotectin done by the referring clinician). They will identify children in whom they consider that IBD is either the working diagnosis or amongst the differential diagnoses.

Consistent with routine clinical practice, children referred to out-patient clinics will be sent a letter including guidance and the consumables required to collect a faecal sample to bring to clinic. Young people or parents/guardians will be asked to collect a stool sample the day before or morning of the clinic visit. They will be instructed to collect 2/3 good scoops of stool using a spatula, or an equivalent volume of liquid stool, into a hard plastic Sterilin tube and wearing a pair of disposable gloves. The tube will be double-bagged using zip lock plastic bags. If collected the day before, they will be asked to store the sealed bag in the home freezer (to stop fermentation) and then bring it to the clinic at ambient temperature. They will be provided with a plastic bag for safe disposal of the consumables used. Children attending the ward for review or directly for investigational procedures will also be requested to provide a stool sample. Stool samples will be used for the measurement of faecal calprotectin for the assessment of intestinal inflammation as part of routine clinical practice.

No additional hospital visits are required to participate in the study. Therefore, no payments (e.g. travel expenses) will be made to participants.

Children who do not meet eligibility criteria at the time of screening will be eligible for rescreening should they present for clinical assessment on a subsequent occasion.

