10.3.2 Primary outcome analysis

For the VOCS identified by GCMS, consistent with our findings in adults (Ahmed 2016), we anticipate identifying a small number of VOCs that can be used to diagnose IBD and distinguish IBD from other common pathologies including functional abdominal conditions.

For the results generated by the GC-sensor (Odoreader©), we will compare the faecal VOC profile in children in whom IBD is confirmed with that in children with alternative diagnoses according to the advanced statistical methods required for determining and comparing VOC profiles (Aggio 2016).

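### The study is sized on VOC specificity exceeding that of faecal calprotectin, but the comparator is a fixed published 0.68 and the primary analysis never compares the two tests

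*Protocol*

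**What the plan says.** - **Sizing (section 10.1).** The rationale is comparative: "we have based the sample size calculation on demonstrating that faecal VOCs have a higher specificity in identifying IBD than FC". The figures follow: "We require 88 children with suspected IBD" to show that "VOCs has a better specificity of 0.80 than the specificity of 0.68 reported for FC", "with 80% power at the 0.05 significance level". Whether the test is one- or two-sided is not stated. The total is then raised to 286, in order to study Crohn's disease versus ulcerative colitis as well.
- **Benchmark (section 1).** The FC specificity is a pooled estimate from a meta-analysis, reported as "0.68 (0.50– 0.86) respectively", where the bracket is the 95% CI.
- **Primary objective, endpoint and analysis (sections 3.1, 3.3, 3.4, 10.3.2).** All concern VOCs in IBD versus non-IBD children. For the GC-sensor, "we will compare the faecal VOC profile in children in whom IBD is confirmed with that in children with alternative diagnoses". For GCMS, the aim is to find a few discriminating compounds. Neither names FC or 0.68.
- **FC in the study.** Section 7.1.2 says "Stool samples will be used for the measurement of faecal calprotectin for the assessment of intestinal inflammation as part of routine clinical practice". Section 7.6 records the result where the test was done. The only planned analytic use is in section 10.9, which explores whether adding FC to VOCs improves accuracy.

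**The concern.** The hypothesis that sets the sample size and the hypothesis that the primary analysis addresses are different. The first is about two tests; the second is about one test in two groups of children. As the plan stands, the only comparator for VOC specificity is a number from other populations with a wide interval. The target of 0.80 lies inside that interval.

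The FC comparison is the study's clinical motive: section 1 argues that FC's low specificity is why another test is needed. A VOC specificity significantly above 0.68 would be read as VOCs being better than FC. It could instead arise because FC itself performs better in these referred children than in the meta-analysis. If FC performs worse here, a real advantage could be missed.

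The operating point matters to the same reading. Section 10.1 cites FC's sensitivity of 0.98 as the reason for concentrating on specificity. The adult VOC results in section 1 pair specificities of 80–82% with sensitivities of 94–96%. A gain in specificity can therefore be bought with missed IBD unless the two are reported together.

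**Working it through.** **Inputs**
- VOC specificity 0.80, FC specificity 0.68, power 80%, alpha 0.05: section 10.1. Difference = 0.12.
- 95% CI for 0.68 of 0.50 to 0.86: section 1.
- 286 children, IBD in one in two: section 10.1. Non-IBD = 286/2 = 143; section 10.2 agrees (143 IBD cases and a similar number of controls).
- FC sensitivity 0.98: section 10.1.
- Discordance between VOC and FC results in non-IBD children: not in the documents, so assumed over a range.

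**1. Reproduce 88.** One-sample test against a constant, two-sided, variance at the alternative:

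n = (1.960 + 0.8416)² × 0.80 × 0.20 / 0.12² = 7.849 × 0.16 / 0.0144 = 87.2, rounded up to 88.

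Other one-sample versions give 85 (one-sided, null and alternative variances) to 109 (the same, two-sided). A comparison of two independent samples needs 209 per group two-sided, or 165 one-sided. So 88 treats 0.68 as known.

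**2. Power at the planned size against a fixed 0.68.** Two-sided, null variance in the critical value:

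z = (0.12 × √143 − 1.960 × √(0.68 × 0.32)) / √(0.80 × 0.20) = (1.435 − 0.914) / 0.400 = 1.30, so power is 0.90. The exact binomial test gives 0.89.

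**3. What that test says about FC.** It depends on VOC specificity alone. Suppose FC's specificity in these children is also 0.80, which is inside the cited CI. VOCs then have no advantage, but the calculation in step 2 is unchanged. The test still places VOCs above 0.68 in about 89–90% of studies.

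**4. The paired alternative.** McNemar comparison in non-IBD children, two-sided 0.05, with discordance ψ:

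n = (1.960√ψ + 0.8416√(ψ − 0.0144))² / 0.0144

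power at 143 = Φ[(0.12√143 − 1.960√ψ) / √(ψ − 0.0144)]

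| Assumed discordance | Pairs for 80% power | Power with 143 pairs |
|---|---|---|
| 0.12 (minimum, equal to the difference) | 63 | 99% |
| 0.20 | 107 | 90% |
| 0.25 | 134 | 83% |
| 0.264 | 142 | 80% |
| 0.30 | 162 | 75% |
| 0.392 (tests independent: 0.68 × 0.20 + 0.80 × 0.32) | 212 | 63% |

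These figures assume an FC result in every non-IBD child and ignore uncertainty in the VOC threshold.

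**5. Matching VOCs to FC's observed sensitivity.** With sensitivity 0.98, FC would miss 143 × 0.02 = 2.9, or about 3 IBD cases. A VOC threshold set by about 3 children would be unstable.

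**The case against.** **SAP content.** Section 10 announces a separate SAP. The threshold, the test statistic and any handling of multiplicity can properly be left to it. This stands, so the lack of a fixed VOC sensitivity is not a separate defect here. It does not remove the mismatch, because the sizing hypothesis and the primary analysis are both stated in the protocol and differ.

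**VOC specificity will be estimated.** Section 7.11 promises sensitivity, specificity and ROC results, with double cross-validation for the GC-sensor. True, and the estimate could be set beside 0.68. That is the comparison shown in step 3 to say little about FC in these children.

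**The paired comparison has its own weaknesses.** FC is recorded only where it was done, so pairs may be incomplete. Clinicians see referral FC results when identifying children (section 7.1.2), and the blinding in section 7.4 covers VOC results only. If a raised FC prompts entry, FC specificity in the study is depressed and VOCs are favoured. No FC cut-off is stated. All of this stands and shapes the fix.

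**Stronger readings that the documents do not support**
- *The sample size is miscalculated, or true power is about 23%.* The 88 reproduces. The 23% comes from carrying the benchmark's standard error (0.36/3.92 = 0.092) into a test that the protocol does not plan.
- *Two measurement methods inflate the type I error.* Section 3.4 says "Faecal VOCs will be measured in stool samples by two methods", but a 9.75% family-wise rate (1 − 0.95²) assumes two independent 5% tests. Both methods analyse the same stool, and handling of multiplicity may sit in the SAP.
- *The study cannot meet its primary objective.* IBD versus non-IBD discrimination can be answered as planned, and no listed objective claims superiority over FC.

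**Conclusion.** The concern holds as a mismatch between design and analysis, not as an arithmetic error. The study is sized to show that VOCs are more specific than FC, against a constant whose own CI runs from 0.50 to 0.86. No objective, endpoint or primary analysis in the protocol makes that comparison.

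The planned 143 or so non-IBD children give about 90% power to beat a fixed 0.68. Beating it would not show that VOCs beat FC here: with both specificities at 0.80, that result would still appear about 89–90% of the time. A paired comparison in the same children addresses the question directly. Its power at 143 complete pairs ranges from 99% to 63%, and reaches 80% only if discordance is about 0.26 or less. That range rests on assumed discordance, specificities of 0.80 and 0.68, and complete FC data.

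**What to change.** In sections 10.1 and 10.3.2, either:

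1. **Name the comparison.** Make the paired difference in specificity (VOC minus FC) a primary or key analysis.
   - Population: the study's own non-IBD children with both results.
   - Method: McNemar test or paired bootstrap CI, using cross-validated VOC predictions.
   - Operating points: a pre-specified FC cut-off and a pre-specified VOC target sensitivity, with both tests' sensitivities reported alongside. Do not match the VOC threshold to FC's observed sensitivity.
   - Power: restate it for 143 complete pairs as a range over assumed discordance (99% at 0.12, about 80% at 0.26, 63% at 0.39), noting that missing FC lowers it.
   - Reporting: FC completeness, and results by whether FC was known at referral, with a statement that this does not fully remove selection on FC. Keep 0.68 as context only.

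2. **Or change the rationale.** Drop superiority over FC and justify the sample size for the IBD versus non-IBD objective actually analysed.

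The cost is a less favourable stated power and, under option 1, one added analysis on data already collected. No extra visits or samples are needed.
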